7.15. Triggered Requirements for Monitoring

For additional Czech Republic, Spain and United Kingdom-specific laboratory criteria, see [Appendix 5](#).

Condition	Action
Neutrophil counts <1000 cells/mm ³	The subject should return to the study site for prompt retesting.
Persistent neutrophil counts of 500-1000 cells/mm ³	Interrupt study drug until neutrophil count is greater than or equal to 1000 cells/mm ³
Confirmed neutrophil counts <500 cells/mm ³ by repeat testing	Discontinue study drug and follow to resolution.
Lymphocyte counts <1000 cells/mm ³	The subject should return to the study site for prompt retesting.
Confirmed lymphocyte counts <500 lymphocytes/mm ³ by repeat testing	Discontinue study drug and follow to resolution.
Any single AST and/or ALT elevation ≥3 x ULN	The subject must return to the study site for prompt retesting and include the following tests: albumin, creatine kinase (CK), total bilirubin, direct and indirect bilirubin, GGT, PT/INR, and alkaline phosphatase.
2 sequential AST or ALT elevations ≥3 x ULN with a total bilirubin value ≥2 x ULN	
 • If drug-induced liver injury is suspected, interrupt study drug until the diagnosis is excluded. • The subject must return to the study site for prompt retesting and include the following tests: albumin, creatine kinase (CK), total bilirubin, direct and indirect bilirubin, GGT, PT/INR, and alkaline phosphatase. • Additional investigations include a detailed history, occupational exposure, sexual history, travel history, history of contact with a jaundiced subject, surgery, blood transfusion, history of liver or allergic disease, work exposure, history of ethanol, recreational drug and dietary supplement consumption. Testing for acute hepatitis A, B or C infection and biliary tract imaging may be considered. • Conduct study visits until end of study.
2 sequential AST or ALT elevations ≥3 x ULN with an abnormal INR	
 • Permanently withdraw the subject from the study drug and follow to resolution. • The subject must return to the study site for prompt retesting and include the following tests: albumin, creatine kinase (CK), total bilirubin, direct and indirect bilirubin, GGT, PT/INR, and alkaline phosphatase. • Additional investigations include a detailed history, occupational exposure, sexual history, travel history, history of contact with a jaundiced subject, surgery, blood transfusion, history of liver or allergic disease, work exposure, history of ethanol, recreational drug and dietary supplement consumption. Testing for acute hepatitis A, B or C infection and biliary tract imaging may be considered. • Conduct study visits until end of study.

Condition	Action
2 sequential AST or ALT elevations ≥ 3 x ULN accompanied by symptoms consistent with hepatic injury	
 • Permanently withdraw the subject from the study drug and follow to resolution. • The subject must return to the study site for prompt retesting and include the following tests: albumin, creatine kinase (CK), total bilirubin, direct and indirect bilirubin, GGT, PT/INR, and alkaline phosphatase. • Additional investigations include a detailed history, occupational exposure, sexual history, travel history, history of contact with a jaundiced subject, surgery, blood transfusion, history of liver or allergic disease, work exposure, history of ethanol, recreational drug and dietary supplement consumption. Testing for acute hepatitis A, B or C infection and biliary tract imaging may be considered. • Conduct study visits until end of study.
2 sequential AST or ALT elevations ≥ 5 x ULN, regardless of Total Bilirubin or accompanying symptoms	
 • Permanently withdraw the subject from the study drug and follow to resolution. • The subject must return to the study site for prompt retesting and include the following tests: albumin, creatine kinase (CK), total bilirubin, direct and indirect bilirubin, GGT, PT/INR, and alkaline phosphatase. • Additional investigations include a detailed history, occupational exposure, sexual history, travel history, history of contact with a jaundiced subject, surgery, blood transfusion, history of liver or allergic disease, work exposure, history of ethanol, recreational drug and dietary supplement consumption. Testing for acute hepatitis A, B or C infection and biliary tract imaging may be considered. • Conduct study visits until end of study.
Increased lipid parameters (total cholesterol, LDL cholesterol, HDL cholesterol, triglycerides)	Monitor and treat according to local guidance (eg, diet and behavior modification, statin therapy).
Hemoglobin < 8.0 g/dL or a decrease of ≥ 2 g/dL compared to baseline, confirmed by repeat testing	Interrupt the administration of study drug until hemoglobin values have normalized.
Serious infections (those requiring hospitalization and/or those requiring parenteral antimicrobials)	Interrupt study drug until the infection is controlled.
Surgery	Interrupt study drug 2 weeks prior to a scheduled surgical procedure and may resume when operative site is sufficiently healed and risk of infection is minimal.
Subjects who cannot be adequately treated for RA within study guidelines	Provide alternate treatment and continue the subject in the study.
Pregnancy or refusal to use appropriate contraception	Permanently withdraw the subject from the study drug and follow any pregnancy to resolution conducting study visits until end of study.
Use of prohibited concomitant medications	See Section 5.5 Concomitant Medication(s) of the protocol for specific actions.

Condition	Action
Anaphylactic or other serious allergic reaction	Immediately discontinue study drug and institute appropriate therapy. Continue subject in study on standard of care treatment and conduct study visits until the end of the study
Symptoms suggestive of a lupus-like syndrome	Discontinue study drug and institute appropriate therapy. Continue subject in study on standard of care treatment and conduct study visits until the end of the study
Vomiting, diarrhea, or if stomatitis occurs, all of which may result in dehydration	Interrupt study drug until recovery occurs.
Interruption of study assigned drug for ≥ 2 months	Must be switched to standard of care treatment

ALT = alanine aminotransferase; AST = aspartate aminotransferase; g/dL = grams per deciliter; GGT = gamma-glutamyl transpeptidase, PT/INR = Prothrombin Time International Normalized Ratio; mm = millimeter; x ULN = times the upper limit of normal

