8.6.2. Potential Cases of Drug-Induced Liver Injury

Abnormal values in aspartate transaminase (AST) and/or alanine transaminase (ALT) concurrent with abnormal elevations in total bilirubin that meet the criteria outlined below in the absence of other causes of liver injury are considered potential cases of drug-induced liver injury (potential Hy's Law cases) and should always be considered important medical events.

Reported transaminase elevations from both AEs and laboratory reports will be reviewed by the study team to identify any potential cases of drug-induced liver injury that occur during the course of the study; all potential cases of drug-induced liver injury will be adjudicated by an external review committee, which may request additional data surrounding the event to assist in the classification of such events (see [Section 9.7.1 Hepatic Event Review Committee](#)). The investigator should refer to the following guidance when evaluating subjects with transaminase elevations.

The threshold of laboratory abnormalities for a potential case of drug-induced liver injury depends on the subject's individual baseline values and underlying conditions. Subjects who present with the following laboratory abnormalities should be evaluated further to definitively determine the etiology of the abnormal laboratory values:

- Subjects with AST or ALT and total bilirubin baseline values within the normal range who subsequently present with AST or ALT ≥ 3 times the upper limit of normal (X ULN) concurrent with a total bilirubin ≥ 2 X ULN with no evidence of hemolysis and an alkaline phosphatase ≤ 2 X ULN or not available;
- For subjects with preexisting ALT **OR** AST **OR** total bilirubin values above the upper limit of normal, the following threshold values should be used in the definition mentioned above:
 - For subjects with pre-existing AST or ALT baseline values above the normal range: AST or ALT ≥ 2 times the baseline values and ≥ 3 X ULN, or ≥ 8 X ULN (whichever is smaller).

Concurrent with

- For subjects with pre-existing values of total bilirubin above the normal range: Total bilirubin increased by one time the upper limit of normal **or** ≥ 3 times the upper limit of normal (whichever is smaller).

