The subject should return to the investigational site and be evaluated as soon as possible, preferably within 48 hours from awareness of the abnormal results. This evaluation should include laboratory tests, detailed history and physical assessment. In addition to repeating AST and ALT, laboratory tests should include albumin, creatine kinase, total bilirubin, direct and indirect bilirubin, gamma-glutamyl transferase, prothrombin time (PT)/INR, and alkaline phosphatase. A detailed history, including relevant information, such as review of ethanol, acetaminophen, recreational drug and supplement consumption, family history, occupational exposure, sexual history, travel history, history of contact with a jaundiced subject, surgery, blood transfusion, history of liver or allergic disease, and work exposure, should be collected. Further testing for acute hepatitis A, B, or C infection and liver imaging (eg, biliary tract) may be warranted. All cases confirmed on repeat testing as meeting the laboratory criteria defined above, with no other cause for LFT abnormalities identified at the time should be considered potential Hy's Law cases irrespective of availability of all the results of the investigations performed to determine etiology of the abnormal LFTs. Such potential Hy's Law cases should be reported as SAEs and study drug should be interrupted at least until the event is resolved.

All potential cases of drug-induced liver injury will be reviewed by the Hepatic Event Review Committee ([Section 9.7.1](#)).

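### Protocol Sections 7.15 and 8.6.2 set different conditions and different end points for interrupting study drug in a potential Hy's Law case, and overlapping liver rows in 7.15 have no stated order of precedence

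*Protocol*

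**What the plan says.** The Protocol Section 7.15 table has four rows for confirmed transaminase elevations.

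- **Bilirubin row.** Two consecutive AST or ALT values at or above 3 x ULN "with a total bilirubin value" at or above 2 x ULN. Drug action: "If drug-induced liver injury is suspected, interrupt study drug until the diagnosis is excluded".
- **INR row.** The same transaminase level "with an abnormal INR". Drug action: "Permanently withdraw the subject from the study drug and follow to resolution".
- **Symptom row.** The same transaminase level "accompanied by symptoms consistent with hepatic injury". Drug action: permanent withdrawal, worded as in the INR row.
- **5 x ULN row.** Two consecutive values at or above 5 x ULN, "regardless of Total Bilirubin or accompanying symptoms". Drug action: permanent withdrawal again.

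A later row of the same table moves a subject to standard of care once study drug has been interrupted for 2 months or more.

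Protocol Section 8.6.2 defines the potential Hy's Law case. For subjects with normal baseline values it uses the same two thresholds (3 x and 2 x ULN), "with no evidence of hemolysis and an alkaline phosphatase" no higher than 2 x ULN or not available. It has separate thresholds for abnormal baselines. Once the pattern is confirmed on repeat testing and no other explanation has been found by then, the case is reportable as an SAE and "study drug should be interrupted at least until the event is resolved". This applies even if some work-up results are still outstanding.

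Table 3 (Section 7.10) points to 7.15 for retesting and to 8.6.2 for managing the elevations. The liver rows of 7.15 do not cite 8.6.2, and 8.6.2 does not cite 7.15.

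**The concern.** A site with a confirmed transaminase-plus-bilirubin result is sent to two sections that do not agree on what makes the interruption necessary or on what ends it. Excluding drug-induced injury and resolution of the event are different milestones and can fall at different times. If the subject also has an abnormal INR, hepatic symptoms or transaminases at or above 5 x ULN, two rows of one table apply together: one reversible and conditional, the other permanent.

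What is at stake is first a patient-safety instruction and its uniform use across sites. The trial is open-label and all subjects are on background methotrexate, so whether drug-induced injury is suspected is a matter of judgement. Second, the choice of text can determine whether a subject returns to randomized treatment at all, because of the 2-month row.

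**Working it through.** The point concerns rules, not figures. The documents state no number to reproduce, so the check is to apply the texts to cases.

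**Step 1: the instructions side by side.**

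| Source | Needed beyond AST/ALT at or above 3 x ULN twice | Drug action | What ends it |
|---|---|---|---|
| 7.15 bilirubin row | Bilirubin at or above 2 x ULN; injury suspected | Interrupt | Diagnosis excluded |
| 8.6.2 | Bilirubin at or above 2 x ULN; hemolysis and alkaline phosphatase conditions met; no other cause found by then | Interrupt | Not before resolution |
| 7.15 INR row | Abnormal INR | Withdraw | Permanent |
| 7.15 symptom row | Hepatic symptoms | Withdraw | Permanent |
| 7.15 5 x ULN row | Transaminase at or above 5 x ULN | Withdraw | Permanent |

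**Step 2: no added finding.** Take ALT 4 x ULN and bilirubin 2.5 x ULN on two tests, with normal INR, no symptoms and no other cause yet found. No permanent-withdrawal row applies. Two instructions meet, the bilirubin row and 8.6.2, and they differ in trigger and end point.

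**Step 3: when the end points separate.** Let t_c be the time from the start of interruption until another cause is established and drug-induced injury excluded, and t_r the time until the event resolves.

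- The bilirubin row ends the pause at t_c; 8.6.2 holds it at least until t_r.
- If t_c < t_r, the texts disagree over the whole interval from t_c to t_r.
- If t_c < 2 months ≤ t_r, the bilirubin row permits return to randomized drug, while the 8.6.2 pause reaches the 2-month row and the subject goes to standard of care.

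**Step 4: overlap inside 7.15.** The bilirubin row has no upper transaminase limit and does not exclude abnormal INR or symptoms.

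- ALT 4 x ULN, bilirubin 2.5 x ULN, plus abnormal INR or symptoms: the bilirubin row and a permanent-withdrawal row both apply, and no wording ranks them.
- ALT 6 x ULN, bilirubin 2.5 x ULN: the bilirubin row and the 5 x ULN row both apply. The phrase "regardless of Total Bilirubin or accompanying symptoms" points to the latter governing, but the table does not say that it displaces the bilirubin row.

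**Step 5: count of logical cases.** Hold fixed: confirmed AST/ALT at or above 3 x ULN, bilirubin at or above 2 x ULN, normal baseline, and the 8.6.2 hemolysis and alkaline phosphatase conditions met. Vary five yes/no factors: transaminase at or above 5 x ULN, abnormal INR, symptoms, injury suspected, other cause identified. That gives 2^5 = 32 combinations.

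- At least one permanent-withdrawal finding: 7 of the 8 transaminase/INR/symptom patterns, so 7 x 4 = 28 combinations.
- Of these 28, the 14 with no other cause identified also meet 8.6.2, so three instructions apply. The other 14 meet two.
- No added finding: 4 combinations. Two meet two instructions (no other cause identified) and two meet only the bilirubin row.
- Totals: 14 with three instructions, 14 + 2 = 16 with two, and 2 with one; 14 + 16 + 2 = 32.

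These count logical situations in which more than one text applies. They are not patient frequencies, and not every co-application is a contradiction (see the objection).

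**Step 6: link to the analysis.** SAP Section 7.1.1 applies on-treatment censoring when a subject changes from randomized treatment to standard of care: last dose plus 60 days for MACE, plus 28 days for secondary safety endpoints. A pause followed by restart does not set that clock. It is set only if drug is not resumed. The primary malignancy analysis uses Total Time and does not depend on last dose.

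**The case against.** A reader might infer that the protocol gives three different drug actions for the same transaminase-plus-bilirubin result, so that one patient could be kept on, paused from or permanently taken off drug according to the line read. The documents do not support that, for three reasons.

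- Permanent withdrawal is never triggered by that result alone. It needs an abnormal INR, symptoms or 5 x ULN.
- No row instructs a site to keep the subject on drug. That is only implied by the bilirubin row when injury is not suspected.
- The 8.6.2 wording sets a minimum, which permanent withdrawal also satisfies, so 8.6.2 does not compete with the withdrawal rows.

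The defence goes further. Section 8.6.2 describes its cases as potential drug-induced injury with no other cause, so a subject who qualifies is in practice one in whom injury is suspected. The bilirubin row is also wider, having no hemolysis, alkaline phosphatase or baseline-adjusted criteria, and its suspicion clause may be meant to separate cases with another evident cause. This largely closes the gap in trigger. It does not close the gap in end point: 8.6.2 fixes case status on what is known at confirmation and states no release if a cause emerges later.

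The sections are also not unconnected, since Table 3 leads from 7.15 to 8.6.2, and 8.6.2 tells investigators to use its guidance when evaluating transaminase elevations. That is a pointer, not a statement of which text governs. For the 5 x ULN row, the phrase setting bilirubin aside largely answers the overlap. The INR and symptom rows have no such phrase.

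**Conclusion.** The inconsistency holds in two parts. First, the 7.15 bilirubin row and Section 8.6.2 set different conditions and different end points for interruption in a potential Hy's Law case. The end point is the firmer part, and it matters when another cause is found before resolution. Second, the bilirubin row overlaps the INR and symptom rows with no stated precedence, and overlaps the 5 x ULN row with precedence suggested but not stated.

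The size in subjects cannot be derived from the documents. A reader might infer a distortion of the on-treatment MACE comparison; none of material size is claimed, because the censoring clock is affected only where drug is not resumed, and nothing shows how often that would occur or that it would differ by arm. The conclusion assumes normal baseline values and that the 8.6.2 hemolysis and alkaline phosphatase conditions are met. It rests on patient safety and uniform site conduct, and takes no view on which clinical rule is right.

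**What to change.** Reconcile the four confirmed-elevation rows of Protocol Section 7.15 with Section 8.6.2 so that one trigger and one end-of-interruption condition apply to the transaminase-plus-bilirubin pattern. State which row governs when a subject meets more than one, or make the rows mutually exclusive. Align the Table 3 pointer in Section 7.10 so that sites are sent to the governing text. The sponsor's hepatic and safety experts should choose the rule; none is proposed here. The cost is a table edit and matching text in a protocol amendment, with a memo to sites. No new tests, visits or data are needed.

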For the **60-Day On-Treatment Time Analyses** of time-to-event, in addition to the foregoing, when a subject changes from the randomized study treatment to standard of care, the subject’s time to event will be considered censored (censoring time = last dose day of randomized study regimen + the attribution window, or the study day of last on-study contact, whichever is earlier). It will be used for the primary safety endpoint MACE but excluding malignancy (excluding Non-melanoma Skin Cancer (NMSC)), and the attribution window will be 60 days. In other words, the censoring time will be the earliest of study day of last on-study contact, study day of death, and last dose day of randomized study regimen plus 60 days.

For the **Total Time Analyses** of time-to-event, the censoring time will follow the four foregoing listed cases, ie, the censoring time will not change when a subject changes from the randomized study treatment to standard of care. In other words, the censoring time will be the earlier of study day of last on-study contact and study day of death.

For the **28-Day On-Treatment Time Analyses** of time-to-event, in addition to the foregoing, when a subject changes from the randomized study treatment to standard of care, the subject's time to event will be considered censored (censoring time = last dose day of randomized study regimen + the attribution window, or the study day of last on-study contact, whichever is earlier). It will be used for all the secondary safety endpoints, and the attribution window will be 28 days. In other words, the censoring time will be the earliest of study day of last on-study contact, study day of death, and last dose day of randomized study regimen plus 28 days.

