8.2.2. Analyses of Other Safety Endpoints

The analyses will be based on the Safety Analysis Set. The 28-Day On-Treatment Time will be applied to all the events of interest, see [Section 7.1.1](#).

The times to the secondary endpoints of opportunistic infection events excluding tuberculosis, tuberculosis, hepatic events, cardiovascular events (MACE and others), serious infections, GI perforations, non-melanoma skin cancers, interstitial lung disease, DVT, PE, ATE, DVT or PE, thromboembolic events (TE) and all-cause mortality will be analyzed by Cox models via univariate model analysis. See [Section 8.1.1](#). The 28-Day On-Treatment Time analysis will be conducted.

The times to herpes zoster events will be analyzed by a multivariate Cox model with region, baseline corticosteroid use, age group, smoking status, treatment as predictors. The 28-Day On-Treatment Time analysis will be conducted.

Unadjusted, or “crude” incidence rates will be calculated as well. Note that the ratios of these rates approximate, but are not exactly equal to, the hazard ratios.

A Surveillance, Epidemiology, and End Results (SEER) analysis of the malignancy endpoint will be conducted. In this analysis, standardized incidence ratio (SIR) for malignancies represents the ratio of the incident number of cases of cancer in the tofacitinib population to the incident number that would be expected if the study population had the same incidence rate as the US population. By way of interpretation, a SIR of more than 1.0 indicates that proportionally more cases of cancer have occurred in the tofacitinib population than the comparator, whereas a SIR of less than 1.0 indicates that proportionally fewer cancer cases have occurred.

The Sponsor has standard (ie, used for all its clinical trials) summary displays and listings for MedDRA-coded adverse events, demography, medical history, length of time in study and discontinuation, concomitant and concurrent medications, physical examination, ECG, laboratory tests, weight, pulse rate, and blood pressure. These standards, called *CaPS (CDISC and Pfizer Standards)*, will be utilized in the reporting of these routine safety variables. For laboratory tests total cholesterol, LDL-c, HDL-c, total cholesterol/HDL-c ratio, LDL-c/HDL-c ratio, Triglyceride, the summary will be produced by subjects on statins, subjects not on statins and subjects on any lower lipid agents including statins.

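### The 28-Day On-Treatment clock runs to one final last dose, so days late in a permitted drug interruption count as at risk only if the drug is later restarted

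*Protocol*

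**What the plan says.** **Interruptions.** Protocol 7.15 has several triggers after which drug is stopped and may be resumed. For serious infection the action is "Interrupt study drug until the infection is controlled". For surgery it is "Interrupt study drug 2 weeks prior to a scheduled surgical procedure and may resume when operative site is sufficiently healed". Low hemoglobin, persistent neutropenia, and vomiting, diarrhea or stomatitis are handled in a similar way. The limit is the last row of the table: at "Interruption of study assigned drug for ≥ 2 months" the subject "Must be switched to standard of care treatment".

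**Censoring.** For the 28-day analysis, the closing sentence of the relevant paragraph in SAP 7.1.1 gives the censoring time as "the earliest of study day of last on-study contact, study day of death, and last dose day of randomized study regimen plus 28 days". The same section assigns this clock to the secondary endpoints: "It will be used for all the secondary safety endpoints, and the attribution window will be 28 days". SAP 8.2.2 repeats it: "The 28-Day On-Treatment Time will be applied to all the events of interest". Those events include pulmonary embolism, DVT, serious infections and all-cause mortality. SAP 8.1.2 takes time at risk for the crude rates from the same section.

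**What is missing.** Neither document says how a gap in dosing is treated in on-treatment time. The opening sentence of the same SAP paragraph ties the extra censoring to a change to standard of care, which is a different condition from the closing formula.

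**The concern.** Whether a subject is at risk on a given day should depend only on what has happened by that day. Under the closing formula it depends on the future. On gap day 29 nobody knows whether drug will be restarted, yet that later restart decides whether the day belongs to the risk set.

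For all-cause death this creates immortal time. A subject who dies in the gap has no later dose and is censored at gap day 28, so the death is not counted. A subject who survives and restarts contributes every gap day.

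For a non-fatal event, counting turns on whether drug is restarted after the event, and in an open-label trial (Protocol 5.2) that decision is made knowing the arm.

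The affected endpoints matter. Pulmonary embolism and mortality are the signals that led to Amendment 8 (Protocol 1.2). Some of the gaps follow infection or surgery, when risk may plausibly be raised.

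**Working it through.** **Inputs from the documents.** The longest resumable gap is just under 2 months, taken here as 60 days (Protocol 7.15). The window W is 28 days for secondary endpoints and 60 days for MACE (SAP 7.1.1). No interruption rate is stated, so there is no figure in the plan to reproduce.

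**Rule.** Censoring day C = min(last contact, death, final dose + W). An event on day t counts if t ≤ C.

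**Worked cases.** The last dose before the gap is on study day 400. Any event falls on gap day 45 (study day 445). Where drug is restarted, this is on gap day 55 (study day 455) and the final dose is on day 1000.

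| Case | W = 28 | W = 60 |
|---|---|---|
| Death on day 445 | C = min(445, 428) = 428; not counted | C = min(445, 460) = 445; counted |
| Non-fatal event on day 445, never restarted | C = 428; not counted | C = 460; counted |
| Same event, drug restarted | C = 1028; counted at 445 | C = 1060; counted at 445 |
| No event, drug restarted | C = 1028; days 429 to 454 at risk | C = 1060; all gap days at risk |

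With W = 28, the 26 days from 429 to 454 are at risk in the last two rows and not in the first two. Only the later restart separates them. With W = 60 the event counts in every case, so the problem is confined to the 28-day clock.

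**The other wording in SAP 7.1.1.**
- *Opening sentence (censor on a change to standard of care).* The death on day 445 comes before any switch, so it counts. A survivor who is switched on day 460 is censored back to 400 + 28 = 428, while a survivor who restarts keeps all the days. The death is treated the opposite way, and the survivors' time still depends on a later decision.
- *Definition (exposure plus window).* Read per dosing episode, day 445 is outside the window for everyone. That reading looks only backwards, but the SAP does not state it and the closing formula contradicts it.

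**Surgery.** With drug stopped 14 days before an operation, gap day 28 falls on post-operative day 28 − 14 = 14. Any later restart puts the gap into the affected range.

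**Size, on assumptions that are not in the documents.** Simulation of 400,000 subjects per scenario: 3.5 years of follow-up, 1 death per 100 patient-years (PY) outside gaps, at most one long gap per subject lasting 35 to 60 days, and all survivors of the gap restarting. The table gives the share of deaths left uncounted by the closing formula.

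| Rate of first long gap per 100 PY | Gap hazard ×1 | ×5 | ×20 | Person-time beyond gap day 28 |
|---|---|---|---|---|
| 2 | 0.1% | 0.5% | 1.8% | 0.10% |
| 5 | 0.3% | 1.1% | 4.2% | about 0.24% |
| 10 | 0.5% | 2.2% | 7.3% | about 0.44% |
| 20 | 0.8% | 3.4% | 11.1% | about 0.75% |

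Hand check of the moderate case (5 per 100 PY, ×5):
- Long gaps per year: (1 − e^(−0.05 × 3.5)) / 3.5 = 0.0459.
- Mean gap time beyond day 28: 47.5 − 28 = 19.5 days = 0.0534 years.
- Share of person-time: 0.0459 × 0.0534 = 0.00245.
- Uncounted deaths relative to baseline deaths: 5 × 0.00245 = 0.0122.
- Extra deaths over the whole gap: 0.0459 × (47.5/365.25) × 4 = 0.0239.
- Share uncounted: 0.0122 / 1.0239 = 1.2%, against 1.1% simulated. The hand figure ignores deaths before the gap and gaps cut off by the end of follow-up.

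**The case against.** **The opening sentence of the SAP paragraph censors only on a switch, so a death in an unswitched gap counts.** This is a fair reading of that sentence, and it means the loss of gap deaths is not certain. It does not rescue the rule. The sentence contradicts the closing formula, and by censoring a later switch back to day 28 it also lets the future decide who is at risk.

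**An event 40 days after the last dose is meant to fall outside a 28-day window.** This stands. The defect is not that such an event is excluded. It is that other subjects' time, and other subjects' events, on the same gap days are included because drug was later restarted.

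**Other outputs pick up the events.** This stands in part. SAP 6.2 lists all deaths whatever the window, but a listing is not a comparison. Protocol 9.2.2 promises both ITT and on-treatment analyses for secondary endpoints other than adverse events and laboratory abnormalities, so a reader should not infer that the 28-day clock is the only analysis ever planned. SAP 8.2.2, however, specifies only the 28-day analysis.

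**A reader might infer that the rule favours tofacitinib,** for example because sites would be slower to restart tofacitinib than a TNF inhibitor after a pulmonary embolism. The documents do not support this. They give no interruption or restart rates by arm. The February 2019 communication concerned 10 mg BID; the DSMB regarded 5 mg BID as still balanced against TNFi, and subjects on 10 mg BID were to continue on 5 mg BID (Protocol 1.2). If every arm loses the same share of its deaths, the hazard ratio barely moves.

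**Conclusion.** The point holds as a defect in the counting rule. Under the closing formula of SAP 7.1.1, gap days after day 28 are at risk only when drug is later restarted. For death they can add time and never an event; for non-fatal events, counting depends on a decision made after the event. The section also contains a conflicting sentence that does not cure this.

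The size is unknown. On the assumed rates, about 0.1% to 11% of deaths are uncounted, about 1% in the moderate case, so the effect is probably small unless long gaps are common and events cluster in them. No direction between arms is shown.

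The co-primary analyses are essentially unaffected: malignancy uses Total Time, and the 60-day MACE window covers nearly all of a gap shorter than 2 months. Nothing here bears on whether the clinical interruption rule is right.

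**What to change.** In SAP 7.1.1, replace the conflicting sentences with one rule based only on past dosing. A subject is on treatment through 28 days after the most recent dose of randomized drug. Later days are off treatment, with time and events both removed, until the day of restart, whether or not a restart follows. Apply this to the secondary-endpoint Cox models and crude rates through start-stop records, and list by arm the events that fall in gaps. The SAP should also say whether a restarter who had a non-fatal event in a gap re-enters the risk set for a first event.

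This removes the immortal time and the restart-dependent counting. It does not bring gap deaths into the on-treatment analysis, and it should not be presented as doing so. Those deaths enter a comparison only through an ITT (Total Time) analysis, so Protocol 9.2.2 and SAP 8.2.2 should be reconciled as well.

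The cost is SAP wording and minor programming. Protocol 5.3.5 and 5.6.1 already require missed doses and time on treatment to be documented, so no new data should be needed if stop and restart dates can be derived from those records. The downsides are slightly less person-time (about 0.1% to 0.75% in the scenarios above) and the exclusion of a few gap events in restarters that the closing formula now counts.
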